8. PROTOCOL SPECIFIC TRAINING REQUIREMENTS

8.1 MRI Training

- The study PI presented the MRI protocol for review and discussion with the MRI technologists and associated study coordinators during the Investigator meeting held at the 2013, 2014 and 2015 Annual Research Base NCORP Meeting.

Prior to the start of participant enrollment into the study, Wake Forest University Medical Center cardiology imaging specialists observe and continue MRI training at each of the study locations.

Each site will be required to submit two satisfactorily performed studies to the image coordinating center at Wake Forest before initiating the study per protocol 98213 requirements.

8.2 ECHO Training

- For ECHOs, the field site sonographers will be trained in the study protocol by the Wake Forest Echo Core Lab Director ([name]) and chief sonographer ([name], RDMS) prior to study launch using written, illustrated sonographer instructions, a teaching video, didactic sessions, practice patients, field site visits, and 2 final qualifying test cases.

9. SPECIMEN MANAGEMENT

9.1 Lab Corp: Troponin-I at 2 months

Lab Corp will be utilized for all labs. LabCorp couriers will deploy to each site from local LabCorp facilities for specimen pick-up as samples are drawn. All specimens should be collected in containers provided by LabCorp. Note storage times and temperature instructions for each test.

9.2 Collection and Handling Procedures

Refer to Appendix Lab Instructions.

10. REPORTING ADVERSE EVENTS

- A list of adverse events/serious adverse events that have occurred or might occur that are related to this study intervention can be found in Section 6.2.
- Adverse Event/Serious Adverse Event reporting begins after the informed consent is signed.
- Serious Adverse Events occurring within 30 days of study completion must be reported via FDA Form 3500 (MedWatch).

10.1 Protocol Specific Reporting for Adverse Events (AEs)

- DEFINITION: An adverse event (AE) is any untoward medical occurrence in a study participant.
- **Grades 1, 2, and 3 expected (solicited) and unexpected (unsolicited) AEs that meet the above definition for an AE and are ONLY definitely related, possibly related or probably related to this study intervention should be reported to the RB DMC using the Toxicity Assessment Sheet.**

10.2 Protocol Specific Reporting for Serious Adverse Events (SAEs)

DEFINITION: ICH Guideline E2A and Fed. Reg. 62, Oct. 7, 1997 define serious adverse events as those events that meet any of the following criteria?

- Results in death
- Is life threatening (Note: the term life threatening refers to an event in which the patient was at risk of death at the time of the event; it does not refer to an event that hypothetically might have caused death if it were more severe).
- Requires inpatient hospitalization or prolongation of existing hospitalization
- Results in persistent or significant incapacity or substantial disruption of the ability to conduct normal life functions.
- Is a congenital abnormality/birth defect.
- Events that may not meet these criteria, but which the investigator finds very unusual and/or potentially serious, will also be reported in the same manner.
- **Grades 3, 4, and 5 expected (solicited) and unexpected (unsolicited) SAEs that meet the above definition for SAEs and/or regardless of attribution (i.e. regardless of whether they are related to this study intervention or not) should be reported to the RB DMC using the FDA Form 3500 (MedWatch).**
- Site staff and/or Principal Investigators will report to the RB Data Management Staff within 24 hours of discovering the details of all unexpected severe, life threatening (grade 4) and/or fatal adverse events (grade 5) if there is reasonable suspicion that the event was definitely, probably, or possibly related to the study intervention.

Otherwise, the MedWatch should be sent to the NCORPRB DMC by fax or email within 10 working days of discovering the details of the SAE.

Hospitalizations that are scheduled for routine treatments and procedures unrelated to study intervention do not need to be reported.

Data Elements to include on the MedWatch are:

- SAE reported date
- CTCAE Term (v4.03)
- Event onset date and event ended date
- Severity grade (use table provided in Section 10.1.3 below)
- Attribution to study intervention (relatedness)
- Action taken with the study participant and intervention
- Outcome of the event
- Comments

10.3 Guidelines to determine grade and severity of AEs and/or SAEs

Identify the adverse event using the NCI Common Terminology Criteria for Adverse Events (CTCAE) version 4.03. The CTCAE provides descriptive terminology and a grading scale for each adverse event listed. A copy of the CTCAE can be found at

http://ctep.cancer.gov/protocolDevelopment/electronic_applications/ctc.htm#ctc_40

AEs will be assessed according to the CTCAE grade associated with the AE term. AEs that do not have a corresponding CTCAE term will be assessed according to the general guidelines for grading used in the CTCAE v4.03. as stated below.

Grade	Severity	Description
1	Mild	Mild; asymptomatic or mild symptoms; clinical or diagnostic observations only; intervention not indicated.
2	Moderate	Moderate; minimal, local or noninvasive intervention indicated; limiting age-appropriate instrumental ADL*.
3	Severe	Severe or medically significant but not immediately life-threatening; Hospitalization or prolongation of hospitalization indicated; disabling; limiting self-care ADL**.
4	Life threatening	Life-threatening consequences; urgent intervention indicated.
5	Fatal	Death related to AE.

Activities of Daily Living (ADL)

- * Instrumental ADL refer to preparing meals, shopping for groceries or clothes, using the telephone, managing money, etc.
- ** Self-care ADL refer to bathing, dressing and undressing, feeding self, using the toilet, taking medications, and not bedridden.

The Research Base Grant PI, Safety and Toxicity Review Committee and/or Study Chair will take appropriate action to inform the membership and statistical personnel of any protocol modifications and/or precautionary measures, if this is warranted.

The RB DMC is responsible for communicating AEs/SAEs to the FDA, WF IRB, the WF Safety and Toxicity Review Committee (STRC) and/or other regulatory agencies as appropriate per agency reporting requirements.

Institutions must comply with their individual Institutional Review Board (IRB) policy regarding submission of documentation of adverse events. All MedWatch reports should be sent to the local IRB in accordance with the local IRB policies.

10.4 Follow-up of SAEs

Site staff should send follow-up reports as requested when additional information is available. Additional information should be entered on the MedWatch form in the appropriate format. Follow-up information should be sent to the RB Data Management Center as soon as available.

SAEs (Grade 4 and/or Grade 5) for this protocol should be followed for those related to the study intervention. Documentation should include:

- PID
- Date of SAE
- Description of the event
- Relationship of the SAE to the study intervention
- Severity
- Intervention/Resolution

11. STUDY MONITORING

11.1 Data Management Schedule

The Eligibility checklist/Registration Form should be completed on-line prior to placing the patient on study. Data forms will be submitted to the WF NCORP Research Base. Mail to [name] or fax to [contact] according to the timetable below.

Form	Submission Schedule
Consent Form, Flow Sheet/Addenda, Fast MRI Encounter Form, ECHO Encounter Form, Self- Report Questionnaires	Baseline – within 14 days of registration
Self-Report Questionnaires	Baseline (+ or - 14 days)
Fast MRI Encounter Form, ECHO Encounter Form, 2-month Self Reporting Questionnaires Flow Sheet/ Addenda, TAS if applicable, Lab – Troponin-1	2 months (+ or - 14 days)
Fast MRI Encounter Form, ECHO Encounter Form, Self-Reporting Questionnaires, Flow Sheet/Addenda	6 months (+ or - 14 days)
Early Withdrawal Form	Participants who withdraw from treatment or study prior to completion. Submit at withdraw.
Screening Form	Every month

11.2 Case Report Forms

Participant data will be collected using protocol-specific case report forms (CRF).

11.3 Source Documents

Source documents are the original signed and dated records of participant information (e.g., the medical record, shadow chart) which may include electronic documents containing all the information related to a participant's protocol participation. Source documents are used to verify the integrity of the study data, to verify participant eligibility, and to verify that mandatory protocol procedures were followed. An investigator and other designated staff are required to prepare and maintain adequate and accurate documentation that records all observations and other data pertinent to the investigation for each individual participating in the study. All data recorded in the research record (including data recorded on CRFs) must originate in the participant's medical record, study record, or other official document sources.

Source documents substantiate CRF information. All participant case records (e.g., flow sheets, clinical records, physician notes, correspondence) must adhere to the following standards:

- Clearly labeled in accordance with HIPAA practices so that they can be associated with a particular participant or PID;
- Legibly written in ink;
- Signed and dated in a real time basis by health care practitioner evaluating or treating the participant;
- Correction liquid or tape must not be used in source documents or on CRFs.
- Corrections are made by drawing a single line through the error. Do not obliterate the original entry. Insert the correct information, initial, and date the entry.

All laboratory reports, pathology reports, x-rays, imaging study and scans must have:

- Complete identifying information (name and address of the organization performing, analyzing, and/or reporting the results of the test); and
- Range of normal values for each result listed.

11.4 Data and Safety Monitoring Board

The Data Safety Monitoring Board meets every six months to review all phase II and phase III protocols. The Board includes members demonstrating experience and expertise in oncology, biological sciences, biostatistics and ethics. The DSMB report is generated by the RB statistician. Areas of review may include the following: Date study Opened; Study Objectives; Patient Accrual; Patient Status and Retention; Study Status; Last Contact Status; Patient Compliance; Number of Biopsies/Labs as needed; Patient Characteristics; Summary of Observed Toxicities; Adverse Events; Date, Event briefly described, Relationship to Drug, Arm assigned; Summary of Primary and Secondary Measures.

11.5 Record retention

Clinical records for all participants, including CRFs, all source documentation (containing evidence to study eligibility, history and physical findings, laboratory data, results of consultations, etc.), as well as IRB records and other regulatory documentation will be retained by the Investigator in a secure storage facility in compliance with HIPAA, OHRP, FDA regulations and guidance, and NCI/DCP requirements unless the standard at the site is more stringent.

11.6 CDUS Reporting

The WF NCORP Research Base Data Management Center will submit quarterly reports to DCP/CTEP by electronic means using the Clinical Data Update System (CDUS)

12. STATISTICAL CONSIDERATIONS

12.1. Study Design/Endpoints

We propose to test the utility of fast MRI scans to identify cardiotoxicity in patients treated with Chemotherapy for BrC or Lymphoma (taking advantage of existing clinical trial resources). This study allows us to address our over-arching goal: to determine the optimal implementation (alone or in combination with other tests) of our fast MRI processes for forecasting CV injury in patients treated with Chemotherapy in community hospitals through performance of a Phase II comparative effectiveness study within an ongoing clinical trial.

Primary endpoints include LVESV, LV end diastolic volume (LVEDV), LV mid-wall circumferential strain, T1 & T2 Mapping, PWV, aortic wall thickness compared between fast MRI & ECHO and Troponins.

12.2. Primary Aims

Specific Aim 1: To determine if baseline to 2-month measures of left ventricular (LV) volumes, T1/T2 times, and/or aortic pulse wave velocity (all acquired within 10 minutes) can predict baseline to 6-month post Chemotherapy deteriorations in LVEF, as measured by a typical 45-min MRI.

Specific Aim 2: To compare the 10-min MRI metrics with both ECHO including PWV and cardiac serum biomarker (Tnl) for predicting baseline to 6 month deteriorations in LVEF.

Specific Aim 3: To use exploratory algorithmic modeling to obtain optimal strategies for determining the combination of metrics (10-min MRI, ECHO, serum biomarkers) at 2-months that predict the 6-month post Chemotherapy deteriorations in CV function.

12.3. Analysis Plan

Aim 1: We will estimate the correlations between the baseline to 2-month changes in 3 measures from the 10-min MRI (LV volumes, T1/T2 times and aortic PWV) and the baseline to 6-month changes in LVEF as measured by a 45-min MRI. With 30 patients available, we will have 80% power to detect a correlation of 0.5 between each of the baseline to 2-month changes in 10-min MRI measures with the baseline to 6-month change in LVEF. To examine whether the variability of the two MRI assessments (10-min and 45-min) is comparable we will calculate variance ratios for different CV measures and determine their comparability (i.e., they will be considered comparable if they fall between 0.8 and 1.2).

Aim 2: The second Aim will focus on determining the association between early changes in our 10-min MRI as well as changes in conventional measures of CV dysfunction including: 45-min MRI, ECHO (including PWV) and cardiac serum biomarker (TnI) at 2-months and 6-month deteriorations in LVEF. In 2 fashions, we will estimate the change in each of the novel and conventional measures after 2-months and determine how well they predict the baseline to 6-month change in LVEF. First, we will estimate the correlation between the baseline to 2-month changes for each measure with the baseline to 6-month change in LVEF. Also, we may fit linear regression models to estimate the relationship of these early changes in measures with the 6-month change in LVEF adjusting for patient level characteristics. Next, we will dichotomize the patients into those who exhibit a drop in LVEF from baseline to 6 months (absolute level of EF below 50% or a 10% or greater drop in LVEF) and those who don't. We will then perform a series of 2 sample t-tests to see whether the mean change after 2 months in LVEF and the other measures is different for patients who exhibit a drop in LVEF at 6 months.

Aim 3: We will fit a series of exploratory multiple logistic regression models where the outcome measure will be the binary variable LVEF drop baseline to 6-months (yes/no) and each model will begin with a key predictor (10-min MRI measures, 45-min MRI measure or ECHO measure) and then we will add in additional clinical and patient level characteristics into the models to determine whether there is a combination of clinical and demographic characteristics that enhance the prediction of LVEF drop for each measure of CV dysfunction. ***We recognize that with a limited sample size these models will provide initial information about variables that may be useful in predicting the outcome of interest.*** In addition, we will consider using alternative model building strategies such as artificial neural network (ANN) in order to determine whether there are combinations of the measures taken at baseline and 2-months that predict a drop in LVEF at 6 months. For these analyses we will have over 80% power to detect correlations of 0.50 between the baseline to 2-month changes in each measure and the baseline to 6-month changes in the outcomes assuming a 2-sided test with $\alpha=0.05$ and 30 patients. In addition, we will have 80% power to detect a difference between groups (those with a 6-month drop in LVEF vs those without a 6-month drop) equal to 1.06 standard deviations for the measure of interest assuming a 2-sided test with $\alpha=0.05$ if roughly half of the patients exhibit a drop in LVEF after 6 months. If only 33% ($n=10$) exhibit a drop at 6-months then we will have 80% power to detect a difference of 1.12 standard deviations. The primary goal of this Aim for this study is to determine which measures exhibit a correlation with the 6-month outcome and show some predictive strength in the logistic regression models. Those measures that meet these criteria will then be considered in Phase II, which will allow us to directly compare the predictive strength of each measure with each other. In Phase II, when our sample size will increase to 150 patients, we will be able to fit more robust statistical models to develop predictive equations for identifying patients at risk for a drop in LVEF based on their initial and 2-month measures. With the larger sample size we will have over 80% power to detect correlations between the predictors and 6-month change in LVEF of 0.23 or larger. In addition, we will be able to mean differences in patients with or without a 6-month drop in LVEF of less than 0.58 standard deviations if at least 20% ($n=30$ out of 150) of the patients exhibit a 6-month drop in LVEF.

12.4. Secondary Analyses:

Additional cost analyses will be performed. Costs for outpatient services will be based on the Outpatient Prospective Payment amounts (nationwide and specific locality) based on Healthcare Common Procedure Codes or Ambulatory Payment Classification groups.^{xxxii} MRI or ECHO will be converted into cost using the Medicare charges.^{xxxiii} ***Direct Medical Costs:*** Medicare diagnosis-related group reimbursement rates will be applied to define hospital costs (nationwide - and area-specific) using the PC Pricer Prospective Payment System estimator. Total procedural times including preparation and recovery time will also be obtained. Other cost data we will analyze includes: procedural complications cost, inflation/discounting, and societal perspectives.^{xxxiv} ***Cumulative Costs:*** Costs will be aggregated by combining direct medical and indirect costs with complication and incidental finding costs to provide a summed follow-up cost for each study participant.

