7. CLINICAL EVALUATIONS AND PROCEDURES

Note: *Fast MRI is embedded in (98213) Baseline and 6 month MRI. Data will be extracted for use in this protocol. Only additional Fast MRI is at 2 months and additional 3D ECHO will be required at 2 and 6 months.*

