7.2. Baseline Evaluations

MRI Variables -

The primary cardiac and vascular outcome measures include LVEF and PWV. LVEF was selected as our primary cardiac outcome because clinically it has been used for >30 years to guide the administration of potentially cardiotoxic chemotherapy.^{xiii,xiv} Also, we will measure LV end diastolic volume, LV end systolic volume, myocardial strain and strain rate, and mass according to published standards and treat them as continuous variables.^{xv,xvi,xvii} Since vascular stiffness is associated with CV events,^{xviii} we will measure PWV because it measures aortic stiffness without reliance on measures of central aortic pressure, is highly reproducible, and it can be very accurately measured with MRI because it does not require external marking of central landmarks.^{xix,xx,xxi} Finally, we will acquire T1 and T2 maps of the LV myocardium that have been shown in other studies to be associated with myocardial injury.^{xxii,xxiii} The fast MRI protocol is short (10 mins.). All MRI scans will be performed after a formal evaluation of the physical performance parameters of the CMR scanner, completed daily using standard manufacturer-recommended evaluation methods with calibration phantoms to ensure consistent measures over time. Each MRI assessment will be blinded to patient identifiers, the corresponding MRI exam, and prior MRI exams of the same measure (a blinded, unpaired read). A complete double reading on 15% of the CMR cases will be performed for quality control. All study participants will be offered benzodiazepines to assist in easing any claustrophobia concerns.

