7.7. Study Parameters Table

Enrollment in PREVENT study should be documented. Fast MRI is embedded in (98213) Baseline and 6 month MRI. Data will be extracted for use in this protocol. PREVENT study data will be made available to the CHI research team.

Evaluation Procedure	Baseline	2 Months	6 Months	Description
Informed Consent	X			
Fast MRI (A)	X	X	X	LV Volumes (incl LV end diastolic volume, LV end systolic volumes), Pulse Wave Velocity, myocardial strain & strain rate, mass, T1 and T2 maps.
Fast MRI Encounter Form	X	X	X	
3D ECHO (A)	X	X	X	LV Volumes, Ejection Fraction (in 2 and 3D), mass, global longitudinal strain (GLS), diastolic function, and pulse wave velocity.
ECHO Encounter Form	X	X	X	
Lab – ultrasensitive Troponin-I		X		
Self-Report Questionnaires	X	X	X	
Flow Sheet/ Addenda	X	X	X	
Toxicity Assessment Sheet (TAS)				If applicable any time during study.
Early Withdrawal Treatment/Consent		Submit this form when a participant withdraws from active treatment or withdraws consent prior to study completion.		
Screening Form		Submit this form every month.		

(A) Must be obtained prior to first chemotherapy treatment

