7.8. Off Treatment Criteria

Participants may stop participating for the following reasons: adverse event or serious adverse event, concomitant medications, medical contraindication, or interruption of chemotherapy due to adverse events or death.

Participants will continue to be followed, if possible, for safety reasons and in order to collect endpoint data according to the schedule of events. The study is designed to account for dropouts due to poor health or death; thus, there will be no replacement of subjects that must drop out of the study after enrollment.

Patients who are unable to have an MRI or ECHO at baseline will not be allowed to continue participation in the study.

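### The 0.8 to 1.2 variance-ratio rule for the 10-min and 45-min MRI is applied to a bare point estimate with an unnamed numerator, so its label can turn on chance or on the analyst's choice (low priority)

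*Combined protocol and SAP*

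**What the plan says.** Section 12.3, Aim 1, first plans correlations between 2-month changes on the fast scan and "the baseline to 6-month changes in LVEF as measured by a 45-min MRI". It then adds a separate check: "To examine whether the variability of the two MRI assessments (10-min and 45-min) is comparable we will calculate variance ratios" for several cardiovascular measures, and "they will be considered comparable if they fall between 0.8 and 1.2".

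No confidence interval, test or error rate is attached to this rule. The documents do not say which scan is the numerator, which visit is used, or whether the variances are of levels or of change scores. The power and sample-size statements in Sections 12.3 and 12.5 cover correlations and group differences only.

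Three other places bear on how the scans are paired:

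- The note opening Section 7 says "Fast MRI is embedded in (98213) Baseline and 6 month MRI", and then "Only additional Fast MRI is at 2 months".
- Section 7.2 has each MRI read blinded to the other exam. It also plans a 15% double read for quality control, which is not linked to the variance ratio.
- Section 7.8 says "there will be no replacement of subjects that must drop out of the study after enrollment".

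**The concern.** A variance ratio estimated from 30 patients has sampling error. A fixed band around 1 on the point estimate takes no account of it, so two scans with the same true variance can be called not comparable by chance, and two with different variances can be called comparable.

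The band is also lopsided on the ratio scale. An estimate of 0.82 passes, but the same data with the scans exchanged give 1/0.82 = 1.22, which fails. As the numerator is unnamed, two analysts could reach opposite labels from one dataset.

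What is at stake is the reading of one descriptive result: whether the fast scan is as variable as the long one. Section 1 says the pilot will help judge whether long scans could be replaced by a rapid one, so the label may be read as evidence on that question.

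**Working it through.** **The plan's own figure.** The only computed figure for Aim 1 is 80% power for a correlation of 0.5 with 30 patients. By Fisher's z: atanh(0.5) × √27 − 1.96 = 0.549 × 5.196 − 1.96 = 0.894, so power is 81.4%. It reproduces, and it is separate from the variance-ratio rule, for which no figure is stated.

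**Inputs.** From Section 12.3: limits 0.8 and 1.2, n = 30. From Section 7: both scans come from the same patients, so the variances are paired. Assumed: bivariate normality, and a between-scan correlation ρ of 0.8 to 0.98, because the documents give none.

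**Formula.** Let W be the estimated ratio and R the true ratio. W falls below w exactly when the sample correlation between X − √w·Y and X + √w·Y is negative (the Pitman-Morgan argument). With q = w/R this gives

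P(W < w) = T₂₉[ (q − 1)√29 / (2√(q(1 − ρ²))) ],

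where T₂₉ is the t distribution function with 29 degrees of freedom.

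**Worked case: R = 1, ρ = 0.9.**

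- Upper limit: 0.2 × 5.385 / (2√(1.2 × 0.19)) = 1.128, so P(W > 1.2) = 0.134.
- Lower limit: −0.2 × 5.385 / (2√(0.8 × 0.19)) = −1.381, so P(W < 0.8) = 0.089.
- Chance failure: 0.134 + 0.089 = 0.223. A simulation at ρ = 0.9 gives the same pass rate (0.777).

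**Numerator.** The label changes on inversion when W lies in 0.80 to 0.833 or in 1.20 to 1.25. The same formula gives the probability of those two strips.

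**Results, n = 30.**

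| ρ (assumed) | 0.8 | 0.9 | 0.95 | 0.965 | 0.98 |
|---|---|---|---|---|---|
| Equal variances, fails by chance | 37% | 22% | 9.5% | 5% | 1.2% |
| Equal variances, label changes if numerator swapped | 9.5% | 9% | 6% | 4% | 1.5% |
| True 1.5-fold difference passes, larger variance in numerator (R = 1.5) | 16% | 9% | 3% | 1.5% | 0.3% |
| True 1.5-fold difference passes, larger variance in denominator (R = 0.667) | 20% | 13% | 6% | 4% | 1% |

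The last two rows show that the rule detects a 1.5-fold difference fairly well, and that its performance also depends on the unnamed numerator.

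**Fewer pairs.** Dropouts are not replaced, so a 6-month or change-score comparison may have fewer than 30 pairs. At an assumed n = 25, chance failure is 42%, 27%, 13%, 7% and 2% for the same values of ρ.

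**What an interval would show.** The paired 95% interval is W × (K ± √(K² − 1)), with K = 1 + 2(1 − r²)t²/(n − 2), r the observed correlation and t = 2.048. For an observed ratio of exactly 1 and r = 0.9, K = 1 + 2 × 0.19 × 4.196/28 = 1.057, which gives 0.71 to 1.40. At r = 0.8, 0.95 and 0.98 the intervals are 0.63 to 1.58, 0.79 to 1.27 and 0.86 to 1.17.

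**The case against.** The strongest reply is that the correlation may be high. The fast scan is embedded in the long exam at baseline and 6 months, so both come from the same patient and visit, and errors shared within a session would raise the correlation further. At 0.98 chance failure is about 1%. This stands as a limit on the size of the problem. It does not settle it: the documents give no correlation, reads are blinded to the other exam, and Section 2.1.1 describes different acquisitions (28 ms against 44 ms temporal resolution). If change scores are meant, the correlation could be lower than for levels. By how much needs error and change SDs that the documents do not give, so no figure is offered.

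The second reply is that nothing hangs on the label. That is right, and it sets the priority. Section 12.3 selects measures for Phase II by correlation and predictive strength, not by this ratio.

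Three stronger readings are tempting but not supported:

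- That equal-variance scans fail 59% of the time. That figure treats the scans as independent samples, whereas they are paired within patients.
- That Aim 1 or its power is undermined. Neither uses the ratio.
- That the rule is wrong because it cannot see a constant bias between scans. It claims to compare variability only, so this limits what it can support and is not an error in it.

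**Conclusion.** The concern holds at low severity. The missing interval, numerator, visit and type of variance are plain from the text. The practical size is less certain: for equal variances and 30 pairs, chance failure ranges from about 37% to about 1% as the assumed correlation rises from 0.8 to 0.98, and reaches 5% only at about 0.965. The numerator ambiguity is the smaller problem at most of these values, at about 10% down to 1.5% of datasets. All figures assume bivariate normal data.

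A reader might infer that the scans are likely to be mislabelled, or that the pilot's main results are at risk. The documents support neither. They support only that a label based on the point estimate alone is not a sound basis for saying that the scans' variability is, or is not, comparable.

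**What to change.** In Section 12.3, Aim 1:

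- Name the numerator (for example fast over 45-min), the visit, and whether the variances are of levels or of change scores.
- Report each ratio as an estimate with its paired (Pitman-Morgan) 95% confidence interval, and do not conclude comparable or not comparable from the point estimate alone.
- If a flag is kept, use reciprocal limits of 0.80 to 1.25 and call it descriptive, beside the interval. Reciprocal limits remove the numerator problem but not the chance failures: equal variances would still fail 32%, 18% and 6% of the time at correlations of 0.8, 0.9 and 0.95. Requiring the whole 95% interval to lie inside 0.80 to 1.25 is not workable either, since equal variances would then pass only 0%, 0.1% and 7% of the time.
- Reconcile the visits. The Section 7 note implies that both scans exist only at baseline and 6 months, while Aim 2 in Section 12.3 lists the 45-min MRI among the 2-month measures.

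Optionally, for measures that both exams yield, add the mean difference and Bland-Altman limits of agreement, since the plan has no agreement analysis. The plan would need to say which measures these are: Section 7.7 lists "Pulse Wave Velocity, myocardial strain & strain rate, mass, T1 and T2 maps" under the fast MRI, but the documents do not list everything that the 45-min exam yields.

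The cost is SAP wording and a little more analysis on scans already planned. The downside is that the pilot gives no firm yes/no verdict on comparability.
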